10.3. Changes to Final Study Protocol

All protocol amendments must be submitted to the ethics committee and Regulatory Authorities if required by local law. Protocol modifications that affect patient safety, the scope of the investigation, or the scientific quality of the study must be approved by the ethics committee before implementation of such modifications to the conduct of the study. If required by local law, such modifications must also be approved by the appropriate regulatory agency prior to implementation.

However, Biogen Idec may, at any time, amend this protocol to eliminate an apparent immediate hazard to a patient. In this case, the appropriate regulatory authorities will be notified subsequent to the modification.

In the event of a protocol modification, the patient consent form may require similar modifications (see Sections [10.1](#) and [10.2](#)).

10.4. Subject Data Protection

Prior to any data collection under this protocol, patients must also provide all authorizations required by local law (e.g., protected health information authorization in the US).

The patient will not be identified by name in the CRF or in any study reports, and these reports will be used for research purposes only. Biogen Idec and designee(s), ethics committees, and various government health agencies may inspect the records of this study. Every effort will be made to keep the patient's personal medical data confidential.

10.5. Internal Safety Review

Safety and Benefit-Risk Management (SABR) and other applicable personnel at Biogen Idec will review all SAEs on a regular basis.

CONFIDENTIAL

The information contained herein may not be used, disclosed, or published without the written consent of Biogen Idec MA Inc.

11. MANAGEMENT AND REPORTING OF ADVERSE EVENTS/ADVERSE REACTIONS

11.1. Definitions

11.1.1. Adverse Event

An AE is any untoward medical occurrence in a patient or clinical trial subject administered a medicinal product and which does not necessarily have a causal relationship with this treatment. An AE can therefore be any unfavorable and unintended sign (e.g., an abnormal laboratory finding), symptom, or disease temporally associated with the use of a medicinal product, whether or not related to the medicinal product. Additionally, AEs are defined to include laboratory abnormalities leading to treatment discontinuation.

11.1.2. Serious Adverse Event

An SAE is any untoward medical occurrence that at any dose:

- results in death
- in the view of the Prescribing Physician, places the patient at immediate risk of death (a life-threatening event); however, this does not include an event that, had it occurred in a more severe form, might have caused death
- requires inpatient hospitalization or prolongation of existing hospitalization
- results in persistent or significant disability/incapacity, or
- results in a congenital anomaly/birth defect.

While MS relapses resulting in hospitalization are considered SAEs, they will not be reported as SAEs in the study unless, in the opinion of the physician, a relapse is complicated by other SAEs.

All opportunistic infections and malignancies should be considered serious and reported as SAEs.

An SAE may also be any other medically important event that, in the opinion of the Prescribing Physician, may jeopardize the patient or may require intervention to prevent one of the other outcomes listed in the definition above. (Examples of such medical events include allergic bronchospasm requiring intensive treatment in an emergency room or convulsions occurring at home that do not require an inpatient hospitalization.)

CONFIDENTIAL

The information contained herein may not be used, disclosed, or published without the written consent of Biogen Idec MA Inc.

11.2. Monitoring and Recording Events

11.2.1. Adverse Events

Nonserious AEs, except for those AEs that lead to discontinuation of DMF (including laboratory abnormalities that lead to discontinuation), will not be collected as part of this study and should follow spontaneous postmarketing rules as per local regulations.

Note: if a patient discontinues DMF due to a laboratory abnormality, all relevant laboratory test results collected during the study (starting with the most recent values prior to initiating DMF) are also to be reported.

11.2.2. Serious Adverse Events

Any SAE experienced by the patient between the time of the first dose of DMF and study completion or premature study withdrawal, or within 30 days of discontinuation of DMF is to be recorded on an SAE Form, regardless of the severity of the event or its relationship to DMF. For patients who discontinue treatment but continue to participate in the study, any malignancy occurring more than 30 days after the last dose of DMF will be treated as an SAE and reported on an SAE form. For reporting timelines and procedures, see Section [11.2.4](#).

11.2.3. All Events

All events must be assessed to determine the following:

- If the event meets the criteria for an SAE as defined in Section [11.1.2](#).
- The relationship of the event to DMF as defined in Section [11.3.1](#).

11.2.4. Immediate Reporting of Serious Adverse Events

In order to adhere to all applicable laws and regulations for reporting an SAE, the study site must formally notify Biogen Idec SABR or designee within 24 hours of becoming aware of the SAE. It is the Prescribing Physician's responsibility to ensure that the SAE reporting information and procedures are used and followed appropriately.

CONFIDENTIAL

The information contained herein may not be used, disclosed, or published without the written consent of Biogen Idec MA Inc.

Reporting Information for SAEs

Any SAE that occurs between the time of the first dose of DMF and study completion or premature study withdrawal, or within 30 days of discontinuation of DMF must be reported to Biogen Idec SABR or designee within 24 hours of the study site becoming aware of the event. For patients who prematurely discontinue treatment with DMF but continue to participate in the study, any malignancy occurring more than 30 days after the last dose of DMF will be treated as an SAE and must be reported to Biogen Idec SABR or designee within 24 hours of the study site staff becoming aware of the event.

A report ***must be submitted*** to Biogen Idec SABR or designee regardless of the following:

- the severity of the event
- the relationship of the event to DMF

To report initial or follow-up information on an SAE, fax or email a completed SAE form to the following:

Refer to the Investigator Site File for fax numbers and email information

11.2.4.1. Deaths

Death is an outcome of an event. The event that resulted in death should be recorded and reported on the Adverse Event CRF. Additionally, the date and cause of death should be reported on the Record of Death CRF. If applicable, death should also be recorded as the reason for treatment discontinuation and/or study withdrawal. All causes of death must be reported as SAEs. The Prescribing Physician should make every effort to obtain and send death certificates and autopsy reports to Biogen Idec SABR or designee.

11.3. Safety Classifications

11.3.1. Relationship of Events to Study Treatment

The following definitions should be considered when evaluating the relationship of AEs and SAEs to DMF:

CONFIDENTIAL

The information contained herein may not be used, disclosed, or published without the written consent of Biogen Idec MA Inc.

Relationship of Event to Commercial Drug	
Not related	An adverse event will be considered “not related” to the use of DMF if there is not a possibility that the event has been caused by DMF. Factors pointing toward this assessment include, but are not limited to: the lack of reasonable temporal relationship between administration of the drug and the event, the presence of a biologically implausible relationship between the product and the adverse event (e.g., the event occurred before administration of drug), or the presence of a more likely alternative explanation for the adverse event.
Related	An adverse event will be considered “related” to the use of DMF if there is a possibility that the event may have been caused by DMF. Factors that point toward this assessment include, but are not limited to: a positive rechallenge, a reasonable temporal sequence between administration of the drug and the event, a known response pattern of the suspected drug, improvement following discontinuation or dose reduction, a biologically plausible relationship between the drug and the adverse event, or a lack of an alternative explanation for the adverse event.

11.3.2. Expectedness of Events

Expectedness of all AEs will be determined by Biogen Idec SABR according to the approved local label.

11.4. Procedures for Handling Special Situations

11.4.1. Overdose

An overdose is any dose of DMF given to a patient or taken by a patient that exceeds the dose described in the local label. Overdoses are not considered AEs; however, all overdoses should be recorded on an Overdose Form and faxed to Biogen Idec SABR or designee within 24 hours. An overdose should be reported even if it does not result in an AE.

11.4.2. Reporting Pregnancy and Coordination With the Pregnancy Registry

The Prescribing Physician should refer to the approved local label for guidance if female patients become pregnant or are considering becoming pregnant during the study.

At each routine visit, female patients of childbearing potential will be asked about their pregnancy status and possible pregnancies/spontaneous abortions since the last visit or contact. Spontaneous abortions are considered to be SAEs and must be reported as such (Section 11.2.4).

A DMF Pregnancy Registry is being conducted independently of this study, and pregnant women who have received DMF since the first day of their last menstrual period prior to conception or at any time during pregnancy (regardless of participation in any studies) will be offered participation in the Registry, in countries where the Registry is conducted. Pregnant women may be dually enrolled in this study and the DMF Pregnancy Registry. If a pregnant female patient received DMF since the first day of her last menstrual period prior to conception or at any time during pregnancy, and if the patient is willing to

CONFIDENTIAL

The information contained herein may not be used, disclosed, or published without the written consent of Biogen Idec MA Inc.

participate, the Prescribing Physician should contact Biogen Idec SABR or designee within 24 hours of the site becoming aware of the pregnancy to initiate the enrollment process (refer to the DMF Registry Brochure for contact details). Note: the patient's consent to participate will be obtained under the DMF Pregnancy Registry protocol (109MS402).

If a pregnant female patient declines participation in the Pregnancy Registry, pregnancy information will be collected under this protocol. The Prescribing Physician should report the pregnancy to Biogen Idec SABR or designee (via fax or email [see Investigator Site File for fax numbers and email information], using the Pregnancy Form) within 24 hours of the site becoming aware of the pregnancy, and should follow the outcome of the pregnancy and provide the outcome to Biogen Idec SABR or designee.

If the partner of a male patient receiving DMF becomes pregnant at any time during the study, the Prescribing Physician should follow the pregnancy outcome and report any congenital anomaly or birth defect as an SAE to Biogen Idec or designee. Pregnant female partners will not be referred to the DMF Pregnancy Registry.

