9.2.1.3. Discontinuation or Withdrawal of Patients from the Study

9.2.1.3.1. Discontinuation of DMF and Continued Participation in the Study

Patients who discontinue treatment with DMF will have the option to continue participating in the study. The Prescribing Physician will record the primary reason for

CONFIDENTIAL

The information contained herein may not be used, disclosed, or published without the written consent of
Biogen Idec MA Inc.

DMF discontinuation, including AEs (including laboratory abnormalities) leading to discontinuation. If the primary reason for discontinuation of DMF was a laboratory finding, the patient's complete history of relevant laboratory values collected during the study (starting with the most recent values prior to initiating DMF [see Section 9.3.1]) is also to be recorded. Information will be collected at routine clinical visits following the standard protocol as described in Section 9.3.2 through 30 days after the last dose. At routine visits thereafter, the standard protocol will also be followed, except SAE data collected will be limited to reports of malignancies. In the event that a patient does not have a routine visit within 6 months after his/her last dose of DMF, the physician will contact the patient by telephone to obtain the information, with the exception of laboratory data and EDSS score.

It should be noted that patients who discontinue treatment with DMF but continue to be followed in the study should have the option of restarting DMF treatment at any time within the 5-year follow-up period. Once a patient has restarted DMF, the information collected should follow the standard protocol.

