Concomitant use of immunomodulatory, immunosuppressive (including corticosteroids), and anti-neoplastic agents, and other approved MS therapies	X	X	X
Concomitant use of hepatotoxic and nephrotoxic agents (e.g., paracetamol, nonsteroidal anti-inflammatory drugs, antibiotics, anticonvulsants, protease inhibitors, diuretics, and lithium)	X	X	X
EDSS score (including Function System Scores and Ambulation Scores), based on neurological examination ⁶	X	X	X
MS relapse information	X	X	X
MSIS-29, EQ-5D and EQ VAS, WPAI-MS, MFIS-5, and healthcare resource consumption questionnaire ⁷	X	X	X
Pregnancy status (patient-reported, female patients)	X	X	X ⁸

CONFIDENTIAL

The information contained herein may not be used, disclosed, or published without the written consent of Biogen Idec MA Inc.

- ¹ If withdrawal from the study occurs during a routine visit, information collected one last time from the patient will follow the standard protocol, if the patient allows. If withdrawal occurs outside of the physician's office, the physician will contact the patient by telephone to obtain information one last time from the patient, with the exception of laboratory results and EDSS score, if the patient allows.
- ² If a patient does not have a routine visit within 6 months after the last dose of DMF, the physician will contact the patient by telephone to obtain information, with the exception of laboratory results and EDSS score.
- ³ MS relapses resulting in hospitalization will not be reported as SAEs in this study unless, in the opinion of the physician, a relapse is complicated by other SAEs. All opportunistic infections and malignancies should be considered serious and reported as SAEs.
- ⁴ All SAEs that occur within 30 days after the last dose will be collected. Thereafter, AE data collection will be limited to reports of malignancies.
- ⁵ US sites will be asked to conduct blood draws for CBC (not more frequently than every 12 months unless indicated per local standard of care) and to report the results. Physicians in the European Union and Rest of World will be asked to record CBC, liver function, renal function, and urinalysis results *if collected as part of routine clinical practice*. Additionally, if a patient discontinues DMF due to a laboratory abnormality, physicians will be asked to record all relevant laboratory test results collected during the course of the study as part of routine clinical practice.
- ⁶ When collected as part of routine clinical practice.

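### The protocol does not settle whether spontaneous abortions and birth defects arising more than 30 days after the last DMF dose are SAEs

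*Protocol*

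**What the plan says.** **Rules that make the event an SAE.** Section 11.4.2 has female patients of childbearing potential asked about pregnancies and losses at each routine visit. It states: "Spontaneous abortions are considered to be SAEs and must be reported as such", and refers the site to Section 11.2.4. No time limit is attached. Section 11.1.2 lists among the SAE criteria an event that "results in a congenital anomaly/birth defect".

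**Rules that close SAE collection.** Section 9.2.1.3.1 covers patients who stop DMF but stay in the study. Full collection runs through 30 days after the last dose, and then: "At routine visits thereafter, the standard protocol will also be followed, except SAE data collected will be limited to reports of malignancies". Table 7, chart 2, footnote 4 says the same: "Thereafter, AE data collection will be limited to reports of malignancies". Sections 11.2.2 and 11.2.4 name one later exception, under which "any malignancy occurring more than 30 days after the last dose of DMF will be treated as an SAE". Neither mentions pregnancy. The comment to Section 5 of the ENCePP checklist (Annex 2) gives a different limit for safety outcomes other than malignancies: 6 months after the last dose.

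**Separate pregnancy routes.** Section 11.4.2 offers exposed women the DMF Pregnancy Registry in countries where it is conducted. It continues: "If a pregnant female patient declines participation in the Pregnancy Registry, pregnancy information will be collected under this protocol". In that case the physician files a Pregnancy Form, follows the pregnancy and reports the outcome. For a male patient's partner, the physician is to "report any congenital anomaly or birth defect as an SAE to Biogen Idec or designee". No 30-day limit is stated for any of these routes.

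**The concern.** The primary endpoint (Section 9.1.1) is the incidence and incidence rate of treatment-emergent SAEs and of AEs leading to discontinuation. A woman who stops DMF and has a miscarriage more than 30 days later has an event that Section 11.4.2 requires as an SAE and that Section 9.2.1.3.1 and Table 7 exclude. The same holds for a birth defect found at delivery, through Section 11.1.2.

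Two sites with identical patients can therefore file different reports, each following the protocol. This affects the count of pregnancy-related SAEs, the person-time that belongs with that count, and whether the 24-hour SAE reporting duty in Section 11.2.4 applies to the event. The analysis definitions do not resolve it. Section 9.7.3 sets no upper time limit for a treatment-emergent event, and it adjusts the rate for the duration of follow-up for the particular event, which is exactly what is left open.

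**Working it through.** **1. The rules side by side, for an event more than 30 days after the last dose in a patient still in the study**

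| Place | Spontaneous abortion | Birth defect |
|---|---|---|
| 11.4.2 (female patient) | SAE, no time limit | no explicit SAE instruction |
| 11.1.2 | – | SAE by definition |
| 9.2.1.3.1 | not collected as SAE | not collected as SAE |
| Table 7, footnote 4 | not collected as SAE | not collected as SAE |
| 11.2.2, 11.2.4 | no exception given; opening words ambiguous | same |
| ENCePP checklist, Section 5 comment | collected up to 6 months | collected up to 6 months |

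The ambiguity in 11.2.2 and 11.2.4 is that the window runs from first dose to study completion or withdrawal, *or* within 30 days of discontinuation. Read generously, that has no 30-day limit for patients who stay in the study. The malignancy sentence that follows would then be redundant, and 9.2.1.3.1 and Table 7 would still contradict it.

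Table 7, chart 2, contains the conflict in one column. At subsequent routine visits after the last dose, pregnancy status is marked, the SAE row is blank, and only malignancy reports are marked.

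**2. Timing**

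The protocol gives no figure to reproduce. Assumptions not in the documents: DMF is stopped at gestational week *w*, term is week 40 (280 days), and a birth defect is dated at delivery.

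The 30-day window closes at week (7*w* + 30)/7:

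- *w* = 4: 58/7 = week 8.3
- *w* = 6: 72/7 = week 10.3
- *w* = 8: 86/7 = week 12.3
- *w* = 12: 114/7 = week 16.3

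A term birth is inside only if 7*w* + 30 ≥ 280, so *w* ≥ 250/7 = 35.7. After any earlier stop, a defect found at term lies outside.

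Taking the checklist's 6 months as 26 weeks, the window closes at week *w* + 26, that is, week 30 to 38 for a stop at week 4 to 12. A term birth is inside for *w* ≥ 40 − 26 = 14. The choice between the two stated windows therefore moves the cut-off for the last dose from about week 36 to about week 14.

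**3. Spontaneous abortions**

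With an assumed cut-off for losses at week 20 (140 days), the 30 days cover 30/(140 − 7*w*) of the time still at risk: 30/112 = 27% for *w* = 4 and 30/56 = 54% for *w* = 12. These are shares of time, not of losses. The documents give no distribution of losses over gestation, so the share of losses outside the window cannot be derived.

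**4. The alternative routes**

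The Registry is run independently of this study, under its own protocol and consent, and no passage says its outcomes enter this study's SAE tables. The Pregnancy Form, with outcome follow-up, is conditional on the patient declining the Registry. Where no Registry is conducted there is nothing to decline. Section 11.5 still requires all pregnancies to be recorded, but it states no follow-up of the outcome.

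**The case against.** The strongest reply is that classification is at stake, not ascertainment. Exposed women are offered the Registry; those who decline get a Pregnancy Form and outcome follow-up; neither route stops at 30 days; and pregnancy status is asked at every visit after the last dose. This stands. A reader might infer that most outcomes of exposed pregnancies are lost, and the documents do not support that. Outcomes outside the SAE window can be captured elsewhere, the protocol does not say that DMF is stopped in pregnancy, and no majority can be shown for spontaneous abortions. What the reply does not settle is whether these outcomes count as SAEs here, or what happens to maternal outcomes where there is no Registry.

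A second reply is that 11.4.2 belongs to the special-situation procedures, so a site may reasonably let it override the general limit. That is a fair reading, but the protocol does not state it. Section 11.4.2 also sends the site to 11.2.4, which names only malignancy as a later exception.

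A third is that the date of a birth defect is open: the rules go by when an event occurs, and a defect may be found or dated before delivery. This stands as a limit on the term-birth arithmetic.

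Finally, the explicit birth-defect instruction for male patients' partners might look like unequal treatment of mothers and fathers. It has a plain explanation: partners are not referred to the Registry, so they need an instruction within this study.

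**Conclusion.** The conflict holds as one of SAE classification and collection. Section 11.4.2 (spontaneous abortions) and Section 11.1.2 (birth defects) point one way, Section 9.2.1.3.1 and Table 7 point the other, and the checklist gives a third window. The protocol as written supports different SAE counts and different reporting duties for the same event.

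Its size is known only in part. Given a stop during pregnancy, a 40-week term and a defect dated at delivery, term outcomes fall outside the 30-day window unless the last dose is at about week 36 or later. Some later losses fall outside as well, in a share that cannot be stated. The documents give no expected number of pregnancies, so the effect on the overall SAE incidence cannot be computed. The issue does not arise for a patient still taking DMF, or within 30 days of the last dose.

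The missing statement of maternal outcome follow-up where the Registry is not conducted is a second, smaller gap, and it does not depend on the timing assumptions.

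**What to change.** Reconcile Sections 9.2.1.3.1, 11.2.2, 11.2.4 and 11.4.2, Table 7 (chart 2 and footnote 4) and the ENCePP checklist comment. They should state one rule on whether spontaneous abortions and congenital anomalies in DMF-exposed pregnancies, with exposure as defined in 11.4.2, are recorded as SAEs beyond 30 days after the last dose. Exempting them from the malignancy-only limit would agree with 11.4.2 as it stands. Recording them only as pregnancy outcomes would also be coherent, but 11.4.2 would then have to say so. Whichever is chosen, the opening sentence of 11.2.2 and 11.2.4 should be reworded so that it admits one reading.

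In 11.4.2, make the Pregnancy Form and outcome follow-up apply to any exposed pregnant patient who is not enrolled in the Registry for any reason, including where it is not conducted.

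The changes are to wording, but they need a protocol amendment, with the ethics submissions that Section 10.3 requires across about 450 planned sites. The continuing burden is a few more SAE and pregnancy forms, and some outcome follow-up in countries without the Registry. Pregnancy status is already asked at the visits concerned.
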